The proposed exploratory studies will help fill gaps in existing research by determining if female MJ users show changes in CB1R availability when compared to matched controls, and if severity of MJ withdrawal, craving and negative mood during abstinence in MJ users are correlated with CB1R availability. CB1R availability (distribution volume, VT) will be determined for regions associated with mood (amygdala and hippocampus), reward (ventral striatum), cognition (frontal cortex), motor function and learning (cingulate, putamen, and globus pallidus).

Primary objective 1: To examine CB1R availability (VT) in female MJ users and matched controls.

Hypotheses1: When compared to controls, female MJ users will have lower VT, and the magnitude of downregulation will be correlated with greater severity of CUD.

Primary objective 2: To evaluate whether severity of withdrawal during MJ abstinence is negatively associated with CB1R VT in female MJ users.

Hypotheses 2: Greater severity of withdrawal symptoms, negative mood and craving will be correlated with lower VT, particularly in the amygdala and hippocampus.

Secondary objective 3: To examine subjective effects before and after acute MJ administration in MJ users and explore the relationship of these measures to CB1R VT.

Hypothesis 3: Ratings increases in subjective ratings of 'good' and 'take again' for MJ will be inversely correlated with VT in ventral striatum, cingulate, and putamen.

Secondary objective 4: To examine cognitive performance before and after acute MJ administration in MJ users and explore the relationship of these measures to CB1R VT.

Hypothesis 4: MJ will produce impairment of working memory, sustained attention, executive function and planning in MJ users, when compared to their own baseline and when compared to non-drug conditions in controls. We will examine if cognitive performance deficits in response to MJ are correlated with CB1R VT in frontal cortex, cingulate, and putamen.

3. Background (briefly describe pre-clinical and clinical data, current experience with procedures, drug or device, and any other relevant information to justify the research)

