subjects on Spoiled Grass (SPGR) sequenced MRI volumes. VOIs are: ventral striatum, amygdala, putamen, cingulate, globus pallidus, insula, frontal cortex, and hippocampus to target regions associated with drug reward, mood, cognition, motor function and habit learning (see Aims). V_T will be obtained for each VOI by plasma reference graphical analysis (PRGA); we have previously demonstrated that PRGA showed more robust estimates of V_T than the two-compartment model, as measured with time dependency of estimates and the magnitude of inter-subject variability⁽⁸⁾. V_T is a standard outcome for many receptor binding radiopharmaceuticals.

Sample size and Power Analysis: We propose a use of 10 subjects per group (total n=20) to reliably detect CB1R differences in MJ users vs. controls. We completed power analyses with SAS v3.2.2 using our mean and SD ¹¹C-OMAR V_T data, and assuming equal variance per group, we have 95% power for amygdala and globus pallidus, and 80-89% power for putamen, cingulate, insula, frontal cortex, and hippocampus to detect a significant (p<0.05) group difference in V_T of 10% or greater. We will be underpowered to detect 10% change for the ventral striatum (63% power, p<0.05), but this VOI is not one of those hypothesized to be downregulated in withdrawal. Thus, we have sufficient power (\geq 80%, p<0.05) for our study aims.

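### The blanket claim of at least 80% power for the study's aims is broader than its figures: they cover only a 10% group difference, ventral striatum stands at 63%, and the correlations in 10 users have no figure

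*Combined protocol and SAP*

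**What the plan says.** The sample size paragraph in Section 7 proposes 10 subjects per group "to reliably detect CB1R differences in MJ users vs. controls". For a 10% group difference in V_T at p<0.05, it gives 95% power for amygdala and globus pallidus and 80-89% for putamen, cingulate, insula, frontal cortex and hippocampus. For the eighth region it says "We will be underpowered to detect 10% change for the ventral striatum (63% power, p<0.05"), and sets that aside because "this VOI is not one of those hypothesized to be downregulated in withdrawal". The next sentence begins "Thus, we have sufficient power" and extends the 80% conclusion to the study's aims without qualification.

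Section 2 (Objectives) is wider than that calculation:

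- Its target regions include "reward (ventral striatum), cognition (frontal cortex), motor function and learning".
- Hypothesis 1 reads "When compared to controls, female MJ users will have lower VT", with no region excluded. It goes on to predict a correlation between downregulation and CUD severity.
- Primary objective 2 is an association between withdrawal severity and V_T in the female users.

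The Statistical Analysis Plan in Section 7 gives regression models for these associations (Aim 1 and Aim 2), but no effect size and no power.

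**The concern.** There are two gaps between the conclusion and the figures that precede it.

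The first is ventral striatum. The 63% is for the user-control comparison, which is Primary objective 1. The reason for disregarding it concerns withdrawal, which is the subject of Hypothesis 2, and Hypothesis 2 singles out the amygdala and hippocampus. Nothing in Hypothesis 1 exempts ventral striatum.

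The second gap is larger. Primary objective 2 and part of Hypothesis 1 are correlations, and power for a group difference says nothing about them. This paragraph is the only statement of what 10 per group can show. A reader who takes it at its word would treat a null withdrawal correlation as the result of a test with at least 80% power.

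**Working it through.** **Inputs from the documents.** n = 10 per group; p<0.05, sidedness not stated; difference of 10% in V_T; equal variances; stated powers of 95%, 80-89% and 63%; 10 users for the within-user associations. Because sidedness is not stated, both cases are shown.

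**The plan's own figures.** They cannot be reproduced directly, because the V_T means and SDs used are not given. They can be solved backwards. For a two-sample t-test, df = 18 and the noncentrality is d·√(10/2), where d = 10%/CV. Solving for the d that gives each stated power, then CV = 10/d:

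| Stated power | d, two-sided | CV | d, one-sided | CV |
|---|---|---|---|---|
| 95% | 1.706 | 5.86% | 1.531 | 6.53% |
| 89% | 1.508 | 6.63% | 1.336 | 7.49% |
| 80% | 1.325 | 7.55% | 1.156 | 8.65% |
| 63% | 1.083 | 9.23% | 0.919 | 10.88% |

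This neither confirms nor refutes the stated powers. It shows what they imply.

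**Ventral striatum.** The chance of missing a true 10% difference is 100 − 63 = 37%. The difference detectable with 80% power is d(80%) × CV:

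- two-sided: 1.325 × 9.23 = 12.2%
- one-sided: 1.156 × 10.88 = 12.6%

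At the 15% decrease that Section 3 quotes for male users, d = 15/9.23 = 1.625 and power is 93% (one-sided: 15/10.88 = 1.379, 91%). The shortfall therefore concerns the 10% claim, not every plausible effect.

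**Associations within 10 users.** The documents give no expected correlation, so a range is assumed. The test of Pearson's r has n − 2 = 8 df and critical |r| = t/√(8 + t²):

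- two-sided: t = 2.306, so critical |r| = 0.632
- one-sided: t = 1.860, so critical |r| = 0.549

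Power by simulation under bivariate normality (400,000 draws per value):

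| True r (assumed) | Two-sided | One-sided |
|---|---|---|
| 0.3 | 13% | 22% |
| 0.5 | 33% | 46% |
| 0.7 | 68% | 79% |
| 0.71 | 70% | 81% |
| 0.76 | 80% | 88% |

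So 80% power is reached at |r| of about 0.76 two-sided, or about 0.71 one-sided. At r = 0.5 the association is missed 67% of the time two-sided, or 54% one-sided.

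**Why 0.76 is a best case.** It assumes a single predictor and no covariates. The Aim 2 model lists mood, withdrawal and craving scores as independent variables, and the Exploratory Aim paragraph adds propensity-based covariates to all analyses and estrogen/progesterone levels to those of V_T. If each extra term costs one observation, two extra terms leave the equivalent of n = 8, and 80% two-sided power needs a partial |r| of about 0.82. Four leave the equivalent of n = 6 and need about 0.90. Testing several regions and scales with any multiplicity correction would raise these values further.

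**The case against.** The strongest reply is that the plan does not overreach in substance. The sample size paragraph opens by tying n to differences between users and controls. It prints 63% and calls that region underpowered in the sentence before the conclusion. Section 2 introduces the studies as exploratory and names the withdrawal, craving and mood correlations in that same sentence. The abstract calls the project developmental and a first step, and the analysis section speaks of pilot data.

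Much of this stands. It justifies 10 per group, and it means that ventral striatum is disclosed, not hidden. An attentive reader of the paragraph would not be misled about that region's 63%, only about whether the reason for discounting it is sound. Hypothesis 3, which names ventral striatum, adds little: it is secondary and concerns a correlation with subjective ratings, to which the 63% does not apply.

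What does not stand is the unqualified conclusion. Section 2 labels the withdrawal association a Primary objective, and an exploratory purpose does not supply at least 80% power for it.

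It is also fair to say that Aim 1 does not state which participants enter the CUD-severity model. A users-only analysis is the natural reading but is an inference. Aim 2 carries the point without it, since Primary objective 2 is explicitly about the users.

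**Conclusion.** The conclusion should be narrowed. On the plan's own figures it is supported for a 10% group difference in seven of eight regions. It is contradicted by the 63% for ventral striatum under Hypothesis 1, where 80% power starts at a difference of about 12%. It has no support for the within-user associations, where 80% power needs |r| of at least about 0.76 two-sided (0.71 one-sided) and more once the planned predictors and covariates enter. The correlation figures rest on bivariate normality and on assumed true correlations, and the costs of extra terms on one lost observation each.

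Three stronger readings are tempting, and the documents do not support them:

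- **That the statement "we have 95% power for amygdala and globus pallidus" is wrong.** Section 3 gives a test-retest SD of 10%. If that is the SD of a two-scan change with equal, independent errors, scan noise is 10/√2 = 7.1%, above the 5.86% that 95% power implies two-sided (6.53% one-sided). But the 10% comes without sample size or region, from a cited report and not from the data used for the power calculation. If that sample had 7 to 40 people (assumed), the lower 95% limit for the noise would be 4.6% to 5.8%, so 95% power is not excluded. The documents cannot settle this, and it is not part of the finding.
- **That the stated powers contain an arithmetic error.** None is shown. The sentence is too broad for figures that may each be correct.
- **That the study needs more participants.** An exploratory study can proceed with 10 per group if it states what that number can show.

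**What to change.** Keep n and rewrite the closing sentences of the power paragraph:

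1. Limit the statement of at least 80% power, and the wording about reliable detection, to a 10% group difference in the seven regions whose stated power supports it.
2. State that ventral striatum has 63% power at 10% under Hypothesis 1 and reaches 80% only from about 12%. Delete the reason based on withdrawal.
3. State that the within-user associations (Primary objective 2, and the CUD-severity part of Hypothesis 1) are not covered by the power claim. If a detectable |r| of about 0.76 is given, label it a two-sided best case for a single predictor without covariates.
4. Report those associations as exploratory estimates with 95% confidence intervals.
5. While editing, say in Aim 1 which participants enter the CUD-severity model.

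The cost is one rewritten paragraph and a clause in Aim 1, with no change to recruitment, procedures or data collection. The downside is that the stated power becomes less favourable and may draw questions about n.

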Statistical Analysis Plan: Baseline participant characteristics will be summarized and compared between groups (female MJ users vs. controls). For each outcome variable descriptive statistics will be generated; continuous variables will be reported as means (SD) and categorical variables as frequencies and percentages. Outcome variables will undergo data cleansing and evaluated for accuracy and missing data. We will perform exploratory data analyses (stem-leaf displays, box plots, histograms, and Q-Q plots), and, if necessary, appropriate data transformations will be performed. Groups will be matched for age, race, BMI and nicotine use, and we will use propensity score analysis⁽⁸⁵⁾ to evaluate group differences. To compare the groups across different VOIs, we will use a general linear model, where V_T will be the dependent variable with group status (encoded as a dummy variable) as the independent variable, along with covariates for age, race or any other variables indicated by propensity analyses. All VOI-based statistical analyses will be done with SPSS (IBM) statistical software. After the initial VOI-based analyses, we will also use Statistical Parametric Mapping (SPM)^(83, 86) to identify changes of V_T across groups without restrictions of VOIs. The same linear models used in VOI-based analyses will be applied to the voxel-based analyses. We plan to use a threshold level of p = 0.05, FDR-corrected, and the minimal cluster size at 50 voxels (~0.4 ml). Using the SPM package for MATlab, our model will also include fixed and random effects⁽⁸⁷⁾.

Aim 1: To examine the relationship between V_T and severity of CUD, our model will have V_T as the dependent variable, and severity of CUD (number of symptoms on the MINI) as the independent variables.

Aim 2: To determine if VT will be associated with greater withdrawal severity, greater craving and increased negative mood during cannabis abstinence, our model will have V_T as the dependent variable, and assessment instrument scores for mood and MJ withdrawal (MWC)⁽³⁵⁾ and craving (MCQ-SF)⁽⁶⁹⁾ as the independent variables (Hypothesis 2).

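### Does primary objective 1 need a multiplicity and success rule for the eight regional V_T contrasts?

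*Combined protocol and SAP*

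**What the plan says.** Section 2 (Objectives) makes the comparison of V_T between female users and matched controls the first primary objective. Its hypothesis reads: "When compared to controls, female MJ users will have lower VT, and the magnitude of downregulation will be correlated with greater severity of CUD". No region is attached to it. Amygdala and hippocampus are singled out only under Hypothesis 2, for the withdrawal associations.

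Section 7, Derivation of outcome variables, fixes the regions: "VOIs are: ventral striatum, amygdala, putamen, cingulate, globus pallidus, insula, frontal cortex, and hippocampus". The introduction to Section 2 lists seven of these and leaves out the insula.

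The Sample size and Power Analysis paragraph takes 10 per group, p<0.05 and a "group difference in V_T of 10% or greater", and gives power region by region: 95% for amygdala and globus pallidus, 80-89% for five others, 63% for ventral striatum. It sets ventral striatum aside as not among the regions expected to be downregulated in withdrawal, then concludes "Thus, we have sufficient power" for the aims.

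The Statistical Analysis Plan paragraph says "To compare the groups across different VOIs, we will use a general linear model", with V_T as the outcome and group plus covariates as predictors. For the later SPM maps it adds: "We plan to use a threshold level of p = 0.05, FDR-corrected, and the minimal cluster size at 50 voxels". Under Aim 1 it models V_T on the CUD symptom count without naming VOIs.

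**The concern.** The objective is labelled primary and its hypothesis has a direction, yet the plan does not say what result would support it. One VOI out of eight might be enough, or a pattern across regions might be needed. The family itself can be read in more than one way: seven regions in Section 2, eight VOIs in Section 7, or the seven left once ventral striatum is set aside. Multiplicity control is stated for the voxel maps but not for the VOI contrasts, which come first and which the sample size was built on. The severity part of Hypothesis 1 is open in the same way.

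If the loosest reading were used, the false-positive rate for the first primary objective would exceed the nominal level, and the per-region power figures would not describe an adjusted test.

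**Working it through.** **Inputs from Section 7.** Ten per group, p<0.05, a 10% difference, equal variances, eight VOIs, stated power 95%, 80-89% and 63%. The documents give no regional means, SDs or inter-VOI correlations. I assume equicorrelated normal V_T values and show correlations (rho) from 0 to 0.95. I treat 0.7-0.95 as the plausible part, because a participant's VOI values all come from one scan and one plasma input. Two-sided t tests with 18 df are used; the plan states no sidedness.

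**1. The plan's power figures.** Without SDs they cannot be reproduced forward. Solving backwards, with noncentrality d × √(10/2), gives the standardised difference d; the implied between-subject coefficient of variation is 10%/d.

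| Stated power | d | Implied CV |
|---|---|---|
| 95% | 1.706 | 5.9% |
| 89% | 1.508 | 6.6% |
| 80% | 1.325 | 7.6% |
| 63% | 1.083 | 9.2% |

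The documents do not allow these CVs to be checked. They serve only as inputs to step 4.

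**2. False-positive chance if each VOI is tested at 0.05 and any one counts.** Under independence, any direction: 1 − 0.95^8 = 33.7% for eight VOIs and 1 − 0.95^7 = 30.2% for seven. With correlation, by simulation (200,000 null runs per rho):

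| rho | 8 VOIs, any | 8 VOIs, lower | 7 VOIs, any | 7 VOIs, lower |
|---|---|---|---|---|
| 0 | 33.7% | 18.5% | 30.0% | 16.1% |
| 0.5 | 25.9% | 13.0% | 23.7% | 11.8% |
| 0.7 | 19.8% | 10.0% | 18.5% | 9.2% |
| 0.8 | 16.4% | 8.3% | 15.3% | 7.6% |
| 0.9 | 12.4% | 6.2% | 11.8% | 5.9% |
| 0.95 | 9.8% | 4.9% | 9.5% | 4.7% |

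The hypothesis is that V_T is lower, so the relevant figure for eight VOIs is about 5-10%, against 2.5% for one two-sided test.

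**3. Does it matter which list is the family?** At rho 0.7 the lower-V_T figure differs by 10.0 − 9.2 = 0.8 percentage points between eight and seven VOIs; at 0.95, by 4.9 − 4.7 = 0.2. Under equal correlation it makes no difference which region is dropped.

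**4. What an adjustment gains and costs.** Benjamini-Hochberg over eight brings a false lower V_T to 1.5-2.0% for rho 0.95-0.7 (2.6% if independent). Power to find at least one VOI lower, over rho 0-0.95 (100,000 runs each) and with the five middle VOIs all set at 80% or all at 89%:

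| Regions that truly fall 10% | Power after adjustment |
|---|---|
| All | 83-100% |
| Amygdala and hippocampus | 76-92% |
| Amygdala only (stated 95%) | about 76% |
| Hippocampus only (stated 80-89%) | 47-63% |

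Bonferroni (0.05/8 = 0.00625) would take a VOI stated at 95%, 89%, 80% or 63% to about 75%, 61%, 47% or 29%. A VOI at 80% would then need about 17 per group. Covariates are ignored here: losing 3-6 df alone takes 80% to 79-78%, while covariates that explain variance would act the other way.

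**The case for a change.** The strongest case for a change is that the study does not present itself only as exploratory. It has a primary objective, a directional hypothesis and a claim of adequate power, and a plan that makes those claims should say what counts as success. The omission is real and is not a redaction. Even at a correlation of 0.95 the any-direction rate is about twice 5%, and a sentence fixing the family would need no new data or visits.

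Much of this stands. The text names no lead region, and nothing says how the tests combine. Three things weaken it as a reason to change the plan:

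- A threshold does exist. The power paragraph defines a significant group difference at p<0.05, VOI by VOI, so an analyst has a natural default: fit the same model in each listed VOI and report every result.
- The 5-10% needs a rule the plan never adopts, that any single VOI is enough. The 33.7% also needs independence, which is implausible for values sharing one scan and one plasma input.
- Correcting an unrestricted voxel search but not a short list written beforehand is not inconsistent.

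The available remedies are also choices of preference. Benjamini-Hochberg loses power where an effect is confined to one region. A single named region or a composite tested at 0.05 needs no adjustment, but Hypothesis 1 gives no ground for choosing one. Treating the CUD-severity association as merely exploratory would rewrite part of that hypothesis, which closing a multiplicity gap does not require.

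**Conclusion.** No change follows. The plan leaves a rule unwritten that it could have written, but analysts can fill the gap sensibly by reporting all eight listed VOI contrasts under the common model. A reader who sees all eight can judge whether an isolated result amounts to support. The Abstract calls the project developmental, Section 2 calls the studies exploratory, and the Exploratory Aim paragraph calls the data pilot data for planning later work, so little turns on a formal declaration of success.

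The possible inflation is about 5-10% against 2.5% for a false finding of lower V_T. It rests on the any-one-VOI reading and on assumed correlations of 0.95-0.7. On the other side is a power loss from 80-89% to about 47-63% for the hippocampus if it alone changes, taking the stated powers at face value. That is a fair trade-off at 20 participants. Reconciling the insula and ventral striatum across the lists, or labelling the power figures as per VOI and unadjusted, would tidy the text but change no result. The judgement would differ for a confirmatory study, or if a report showed only the VOIs that reached p<0.05.

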Exploratory Aim: For cognitive tasks and subjective effects, we will use ANOVA and linear regression to compare the groups. These pilot data in females will be pooled with our historic samples to generate effect sizes and power analysis for future sex differences research. For all analyses we will add covariates as based on propensity analyses. Levels of estrogen/progesterone will be included for analyses of V_T.

8. Risks

a. Medical risks, listing all procedures, their major and minor risks and expected frequency.

This study involves several separate procedures, each of which entails some risk of discomfort or side effects. These risks are discussed by procedure. Participants will receive a thorough description of all potential risks in the consent document.

Screening procedures: This study involves questions about dangerous or illegal behavior, psychiatric history, a medical history, and a physical exam. There is risk of a possible breach of confidentiality. There is also a small risk that participants will become upset during the screening interview. Participants' names will be recorded only on the screening, informed consent, and necessary medical and payment forms. Anonymous participant identification numbers will be used on all other forms and labeling of biological fluids and test results.

ECG Screening. Although cannabinoids in general do not have an ECG indicated for their prescription, a 12-lead ECG will be conducted in those that appear to meet all other study inclusion/exclusion criteria as an additional screening procedure. These screening ECG results may identify a potentially clinically significant cardiac abnormality (i.e., incidental finding). The screening ECG only identifies an "incidental finding" and is not a full diagnostic ECG. One of the study physicians will contact the participant and discuss the nature of the ECG findings, and if results are clinically significant, the physician will recommend that the participant see his/her physician for diagnostic evaluations, or if needed, refer the participant to an appropriate physician. We will provide a copy of the ECG report. Participants that have clinically relevant ECG abnormalities will be excluded from further study participation. Disclosure of these incidental findings to the participant may be distressing to the participant.

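### The power statement claims at least 80% for the study's aims but calculates it only for the user-control comparison; the Aim 2 correlation within 10 users has no calculation and reaches 80% only at a true |r| of about 0.76

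*Combined protocol and SAP*

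**What the plan says.** **Power (section 7, Sample size and Power Analysis).** The sample size is justified by one comparison: "We propose a use of 10 subjects per group (total n=20) to reliably detect CB1R differences in MJ users vs. controls". The calculation gives power "to detect a significant (p<0.05) group difference in V_T of 10% or greater": 95% for amygdala and globus pallidus, 80-89% for five other regions and 63% for ventral striatum. The paragraph then ends by claiming at least 80% power for the study aims in general.

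**Objectives (section 2).** The association of withdrawal severity with V_T in female users is the second of two primary objectives. Hypothesis 2 reads: "Greater severity of withdrawal symptoms, negative mood and craving will be correlated with lower VT, particularly in the amygdala and hippocampus". The same section introduces the work this way: "The proposed exploratory studies will help fill gaps in existing research".

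**Analysis (section 7, Statistical Analysis Plan).** For Aim 2, "our model will have V_T as the dependent variable, and assessment instrument scores for mood and MJ withdrawal" (MWC) and craving (MCQ-SF) as independent variables. For Aim 1 the same construction is used with a single predictor: "severity of CUD (number of symptoms on the MINI) as the independent variables". The Exploratory Aim paragraph adds: "Levels of estrogen/progesterone will be included for analyses of V_T".

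**The concern.** Only the users go through monitored abstinence, so Aim 2 rests on 10 women, not 20, and on a correlation, not a difference in means. Power for a 10% mean difference says nothing about power for that correlation. A reader of the sample size paragraph would take a primary objective as powered at 80% when nothing in the plan shows it. A null Aim 2 result could then be read as evidence against the withdrawal hypothesis when it may only reflect n=10.

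The second matter is what Aim 2 will estimate. If mood, withdrawal and craving scores go into one model, each slope is adjusted for the other symptoms, and Hypothesis 2 makes no statement about such slopes. The two forms of analysis can give different answers to the same primary objective.

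**Working it through.** **1. The plan's own figures.** Inputs: 10 per group, p<0.05, a 10% difference and equal variances (sample size paragraph). No mean or SD is printed and sidedness is not stated, so the figures cannot be reproduced directly. Working backwards with a two-sample t-test (18 df, two-sided), d = 10% / (SD/mean) and noncentrality d × √(10/2):

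| Stated power | d needed | Implied SD/mean |
|---|---|---|
| 95% | 1.706 | 5.9% |
| 89% | 1.508 | 6.6% |
| 80% | 1.325 | 7.5% |
| 63% | 1.083 | 9.2% |

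The figures are unverifiable but consistent with one another. They are taken as given below, because the issue is what they cover.

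**2. Aim 2, most favourable case.** n=10, one score, no covariates, two-sided 0.05.

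- Residual df = 10 − 2 = 8, t(0.975, 8) = 2.306.
- Critical |r| = 2.306 / √(2.306² + 8) = 0.632.
- Power by simulation from a bivariate normal distribution: 13% at a true |r| of 0.3, 33% at 0.5, 49% at 0.6, 68% at 0.7, 80% at 0.76.
- Fisher z check: tanh[(1.960 + 0.842) / √(10 − 3)] = tanh(1.059) = 0.785, slightly conservative at this size.
- A one-sided test would still need about 0.70.
- Precision: for an observed r of −0.7, z = −0.867 and SE = 1/√7, so the 95% CI is about −0.92 to −0.13.

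The plan gives no expected correlation, so the values of r are a range and not predictions.

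**3. Hormone terms.** If estrogen and progesterone enter as two terms, 6 df remain. At a raw r of −0.7, the effect on power depends on how much of V_T the hormones explain. The plan does not say; the hormones are assumed unrelated to the score.

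| Hormone R² for V_T | Power, one score |
|---|---|
| 0 | 54% |
| 0.1 | 62% |
| 0.2 | 72% |
| 0.3 | 83% |

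Adjustment can therefore lower or raise power relative to the unadjusted 68%.

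**4. Joint entry estimates something else.** For three scores with common intercorrelation ρ and correlations r₁, r₂, r₃ with V_T, the standardised slope is bᵢ = [rᵢ − ρ·Σr/(1 + 2ρ)] / (1 − ρ). Assume r = −0.6, −0.5, −0.4 and ρ = 0.7. Then Σr = −1.5, ρ·Σr/(1 + 2ρ) = −1.05/2.4 = −0.4375, and the third slope is (−0.4 + 0.4375)/0.3 = +0.125. Its correlation with V_T is negative and its joint slope is positive, in the population and before any sampling error.

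**5. Illustrative power for one slope under joint entry, n=10.** All correlations are assumed.

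| Setting | ρ = 0.3 | ρ = 0.5 | ρ = 0.7 |
|---|---|---|---|
| All three scores at −0.7, two hormones unrelated to V_T (4 df) | 60% | 16% | 8% |
| Same, no hormones (6 df) | 79% | 24% | 11% |
| Withdrawal −0.7, other two −0.3, no hormones (6 df) | not run | not run | 62% |

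The ρ = 0.3 column with equal correlations implies a true R² of 3 × 0.49/1.6 = 0.92. If hormones explain 20% of V_T, the 16% becomes 45% and the 8% becomes 12%.

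**The case against.** Four points can be made for the plan.

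- **Exploratory status.** The work is described as developmental and exploratory, and its data as pilot data for later effect sizes and power analyses. This stands, and it is why the remedy is wording and not a larger sample. It does not make the power conclusion true, because that conclusion is not limited to the group comparison.
- **Separate models are a fair reading.** Aim 1 uses the same plural for one predictor, and the Aim 2 sentence refers to Hypothesis 2, which speaks of correlation. This stands. A reader might infer that the plan commits to fitting three scores plus hormones in 10 women. The documents do not support that; they only fail to rule it out.
- **The loss from joint entry is not general.** This also stands. It is severe if the scores are about equally related to V_T and overlap at 0.5 to 0.7, and small if one score dominates or overlap is low. Nor can hormone adjustment be said to cost power, since the 54% is the zero-effect case.
- **The withdrawal measure is not undefined.** A reader might infer that no score has been chosen. The section on laboratory assessment of withdrawal names the composite Withdrawal Discomfort Score and times imaging to peak withdrawal. What remains open is detail and not part of this point: the exact time point, the mood and craving summaries, and whether the sentence "For all analyses we will add covariates as based on propensity analyses" reaches a users-only model.

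**Conclusion.** The power conclusion is wrong as written. It extends a two-group calculation to a primary objective that rests on a within-group correlation in 10 women. This holds under any reading of the Aim 2 model. In the simplest case 80% power requires a true |r| of about 0.76, assuming bivariate normality and a two-sided 0.05 test with no multiplicity adjustment.

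The modelling point is real but conditional. The wording permits joint entry, which would not estimate the quantities in Hypothesis 2. The size of any loss depends on correlations that the documents do not give, so the joint-model figures are illustrations only.

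A reader might go further and infer that the user-control comparison is underpowered too. Nothing here shows that: the group figures are mutually consistent and are not challenged. This should be fixed before analysis; it does not put the design in question.

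**What to change.** 1. **Sample size paragraph.** Limit the closing sentence to the user-control comparison of V_T in the regions listed, and add, for example: *With n=10 users, the Aim 2 correlations have 80% power only for a true |r| of about 0.76 or more (one score, no covariates, two-sided 0.05); they will be reported as estimates with 95% confidence intervals.*

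2. **Aim 2 analysis.** Replace the model sentence with, for example: *In MJ users only, each score will be entered in a separate model of V_T, and its correlation with V_T and 95% CI reported, with amygdala and hippocampus as lead regions.* Report each correlation with and without estrogen/progesterone adjustment.

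The cost is a less favourable power statement and slightly more analysis, since each correlation is reported twice. Sample size and procedures do not change. The fix does not remove the limit of n=10: power at |r| = 0.7 stays near 68% unadjusted, and an interval as wide as −0.92 to −0.13 must be expected around an observed −0.7.
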